We intend to recruit up to 10 stroke survivors over the course of the study. The stroke survivors will participate in a question and answer formatted discussion with research staff to discuss the usability of the device. The clinical personnel involved in the study will participate in a voluntary feedback session to discuss the usability of the device from a clinician's perspective. We will gather feedback from the clinicians about the device. Due to the voluntary nature of the feedback gathered from clinical personnel, consent will be assumed with participation.

We plan to recruit up to 10 stroke survivors based on the following inclusion/exclusion criteria.

Inclusion Criteria

- 1. Male and female, age 18-80;
- 2. Having had a stroke (ischemic or hemorrhagic) at least 6 months prior to study enrollment:
- 3. Moderate to severe upper-limb motor impairments: score of 15-45 out of 66 on the Fugl-Meyer Scale;
- 4. Community dwelling;
- 5. Able to physically fit in the device.

Exclusion Criteria

1. Current participation in rehabilitation program targeting upper extremity function;

- 2. Cognitive impairment resulting to inability to follow instructions (MMSE ≥ 23 and subject is able to follow the 3-Stage Command) or inability to sustain attention for more than 10 minutes:
- 3. Visual impairments as assessed by the NIH Stroke Scale Visual Field subscale (only subjects with no visual loss will participate in the study);
- 4. Aphasia sufficient to limit comprehension and completion of the treatment protocol;
- 5. No more than moderate impairments in paretic UE sensation, passive range of motion, and pain that would limit ability to engage in therapy;
- 6. Increased muscle tone as indicated by score of >/= 3 on the Modified Ashworth Scale;
- 7. Previous diagnosis of neurological diseases other than stroke;
- 8. Other conditions affecting function of the stroke affected upper limb;
- 9. Individuals who present with the following:
 - open wounds
 - fragile skin
 - active infection

Briefly describe study procedures. Include any local site restrictions, for example, "Subjects enrolled at Partners will not participate in the pharmacokinetic portion of the study." Describe study endpoints.

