Data will be obtained from multiple sources: (1) Interviews of subjects, to obtain demographic information, medical history, and responses to clinical assessments. (2) Clinical examination using standard assessment tools. (3) Feedback surveys that will be filled out by study volunteers to provide the R&D team with feedback concerning the design of the BURT robotic system. (4) Data collected by sensors embedded in the robotic system.

All activities will take place at the Motion Analysis Laboratory (MAL). The study involves up to 21 visits in total within a 7 week period. The total duration may vary within this 7 week period to accommodate missed study visits.

Visit number 1:

Potential subjects who are deemed eligible during initial contact (usually by phone) will be invited to attend an in-person screening to ensure that all inclusion and exclusion criteria are met. The first session will consist of consent and screening of the subject. The procedure will start with the Mini-Mental State Examination (MMSE) for the assessment of an individual's ability to follow instructions sufficiently for the successful completion of study protocol. If the MMSE score is less than 23, the subject will be excluded from the study and the procedure will stop.

Since it is relatively common for people to have impaired decision-making capability after a stroke, prospective study volunteers' decision-making capacity and ability to give consent will be assessed using the University of California at San Diego Brief Assessment of Consent Capacity (UBACC) Questionnaire. If the subject demonstrates that he/she is able to understand the study procedures and provide consent, we will proceed to obtain informed consent. In the event that a potential subject fails the UBACC, they will be excluded from the study.

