Informed consent will be obtained by study staff members who have completed the Partners Healthcare System's human subject protection educational requirements, and the CITI Program in Protection of Human Subjects, in compliance with all Federal regulations regarding such training. Prospective subjects will be interviewed to determine preliminary eligibility. Informed consent will be obtained and subjects will be enrolled in the study prior to any clinical or laboratory testing. Subjects will be given a copy of the IRB approved consent form during the initial interview, and study staff will explain in detail the nature of the informed consent process, study purpose and procedures, time commitments, risks, potential benefits, treatment alternatives, rights as research participants, study staff contact information, confidentiality

procedures, and arrangements for medical care provided in case of injury during the study. Participants will be provided with a signed copy of the completed consent form.

• Visit number 2:

Baseline outcomes assessment battery. The clinical assessment session will last approximately $1 \frac{1}{2}$ to 2 hours. A battery of standardized measures for upper extremity in stroke rehabilitation will be administered. The battery will include: (1) range of motion and muscle strength assessment, (2) spasticity evaluation with the Modified Ashworth Scale, (3) Fugl-Meyer Assessment of upper extremity including pain and sensation subtests, (4) Wolf Motor Function Test and (5) the Motor Activity Log. All are reliable and valid measures of upper extremity motor capacity and function. We will also use the Goal Attainment Scaling to identify specific goals to focus on during the intervention. The Fugl-Meyer is our primary outcome measure and the Goal Attainment Scale our secondary outcome measure. The remaining outcome measures will be exploratory.

• Visit number 3-20:

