Clinical testing will be conducted under the direct and continuous supervision of trained study staff. Subjects will be asked to report all activity-related symptoms of pain or discomfort to the study staff. Research staff/therapists will evaluate pain and report to the PI or site responsible investigator who will make the decision to seek medical advice and care. Subjects will be

supervised, guarded and as necessary, and assisted as needed throughout the study sessions. To prevent excessive fatigue, subjects will be encouraged to take breaks as needed throughout all study procedures. Videos of the session will be stored in locked cabinets and on password protected encrypted computer that only study staff within the Motion Analysis Laboratory have access to.

Describe explicitly the methods for ensuring the safety of subjects. Provide objective criteria for removing a subject from the study, for example, objective criteria for worsening disease/lack of improvement and/or unacceptable adverse events. The inclusion of objective drop criteria is especially important in studies designed with placebo control groups.

Subjects will be screened prior to and during enrollment for contraindications to their participation. The clinical tests used in this study are standard instruments associated with minimal risks, and will be administered by a research therapist experienced in working with this patient population. Clinical evaluations administered prior to the study procedures will be used to help identify impairments that may impact safe participation in BURT use.

Research staff in [name] Analysis Laboratory have extensive experience with the measurement tools (e.g. motion capture, wearable sensors) and intervention devices similar to the one used in this study, and have maintained excellent safety records at SRH and at institutions outside the Partners network. The BURT is an actuated (powered) robot capable of independent motion. This device has many built in safety features including a system controller designed to avoid excessively fast movements of the upper extremity, safety limits set for the estimated interaction forces during arm motions, and two emergency switches to immediately shut off robot power in the event of a malfunction. Subjects will be closely supervised during all assessment and therapy sessions to ensure safety.

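### Exclusion item 5 is worded as a condition for acceptance, so read literally it sorts candidates the wrong way round on sensation, passive range of motion and pain

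*Protocol*

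**What the plan says.** Under Research Design and Methods, the protocol introduces its eligibility list with "We plan to recruit up to 10 stroke survivors based on the following inclusion/exclusion criteria". Item 5 under Exclusion Criteria is "No more than moderate impairments in paretic UE sensation, passive range of motion, and pain that would limit ability to engage in therapy".

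The items near it name the state that keeps a person out. Item 6 is "Increased muscle tone as indicated by score of >/= 3 on the Modified Ashworth Scale" and item 8 is "Other conditions affecting function of the stroke affected upper limb".

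The description of Visit number 1 makes the list operative, since candidates attend an "in-person screening to ensure that all inclusion and exclusion criteria are met".

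Two later places touch on the same domains. The Visit number 2 battery contains a range-of-motion assessment and the "Fugl-Meyer Assessment of upper extremity including pain and sensation subtests". The text on subject safety says "Subjects will be screened prior to and during enrollment for contraindications to their participation" and adds "Clinical evaluations administered prior to the study procedures will be used to help identify impairments that may impact safe participation in BURT use".

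**The concern.** An exclusion item should name the state that disqualifies. Item 5 names the state that qualifies: it sets a ceiling on impairment and then sits under the heading that turns meeting the ceiling into a reason for exclusion. The limit (moderate) is given, but it points the wrong way.

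Staff must answer this item for each candidate. If they follow the wording, they turn away the people the sentence describes as acceptable and have no ground in item 5 for turning away the others. If they follow the evident intent, they depart from the approved text, and the quarterly audits under Monitoring and Quality Assurance check adherence to that text.

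The domains are relevant to this study. The intervention moves the paretic arm with a powered device, subjects are asked to report pain, and the first example under the primary aim concerns the range of motion that the device can achieve.

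**Working it through.** The protocol states no figure on this point, so the check is a comparison of passages.

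**1. Direction of item 5 against the rest of the list.** Of the nine numbered exclusion items, items 1, 4 and 6 to 9 name disqualifying states. Items 2 and 3 open with the disqualifying state and add a passing condition in parentheses. Item 5 is the only one whose main clause is itself a passing condition.

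**2. What each reading does.** Assume that the closing qualifier, about limiting the ability to take part in therapy, governs all three domains. Considering item 5 alone:

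| Candidate's impairment in the three domains | Item 5 as a condition for acceptance | Item 5 literally, as an exclusion |
|---|---|---|
| None that limits therapy | admitted | not excluded |
| Limits therapy, at most moderate in every domain | admitted | excluded |
| Limits therapy, worse than moderate in at least one domain | not admitted | not excluded |

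The readings agree on the first row and give opposite results on the second and third. The inversion therefore concerns people with therapy-limiting impairment, not every candidate.

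**3. Whether another section corrects it.**
- Visit number 2 measures these domains as a baseline outcome battery, after screening, and sets no cut-off.
- The safety text implies that impairment is a concern for safe participation, which supports the inferred direction, but it gives no criterion for any of the three domains.
- Exclusion item 8 concerns other conditions of the limb. Sensory loss, stiffness or pain caused by the stroke itself is not clearly covered.
- Exclusion item 6 concerns muscle tone only.
- Inclusion item 3 (Fugl-Meyer score 15 to 45 out of 66) limits motor impairment only.

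No section restates a limit for sensation, passive range of motion or pain.

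**4. Contrast with item 2.** Its parenthesis gives an MMSE score of 23 or more, which is also a passing condition under the exclusion heading. There the lead-in names the disqualifying state, and both Visit number 1 and Consent Procedures say that a score below 23 excludes. The direction is settled elsewhere. Item 5 has no such second statement.

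**The case against.** The strongest reply is that nobody would apply the literal reading. It would bar people with milder impairment and pass those with severe impairment, in an item that is about impairments limiting therapy. Item 4 uses a similar construction in the right direction, the safety text shows what the concern is, and an experienced research therapist administers the tests. The limit is in the item and the direction can be inferred, so on this view it is a slip of drafting.

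Most of this stands, and it bounds the practical risk. It does not make the rule correct: an eligibility item that works only when staff read it against its own heading is wrong as written, and the safety text offers no criterion to use in its place.

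A reader might infer more than the protocol supports:
- **That severely impaired subjects will be enrolled or harmed.** The document does not show this. Staff will probably infer the intent, contraindication screening may catch some cases, and the device has 510-K clearance, a controller that limits speed, force limits, two emergency switches and close supervision.
- **That joining the three domains with *and* is already a second fault.** Read as a condition for acceptance, the sentence ordinarily means that none of the three exceeds moderate. The question of one domain or all three arises only if the item is rewritten as a failing condition.
- **That items 2 and 5 are equally defective, so that no MMSE score is eligible.** This requires detaching item 2's parenthesis from its lead-in and ignoring the rule stated twice elsewhere.

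**Conclusion.** The point holds as a definite wording error in an eligibility rule that is used at screening. Item 5 describes an acceptable subject under the exclusion heading, and nothing else in the protocol states the criterion correctly.

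Its size is modest. It touches only candidates with therapy-limiting impairment in these domains, in a feasibility study of at most 10 subjects. The number who could be misclassified cannot be estimated, because the protocol gives no frequency for such impairment. No statistical quantity depends on it.

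The conclusion rests on reading the qualifier as applying to all three domains. If it applies to pain alone, the literal exclusion on sensation and passive range of motion would be wider, and the inversion would remain.

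**What to change.** Reconcile item 5 with its heading in one of two ways:

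- move it to the Inclusion Criteria with its wording unchanged; or
- keep it under Exclusion Criteria, restated as a failing condition, and say whether one domain is enough to exclude or all three are needed.

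In either case the investigators should confirm the limit they intend. This review does not propose one.

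As an optional tidy-up, item 2's parenthesis could be labelled as the passing condition, in the way item 3 already makes clear who may take part.

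The cost is a wording amendment. It adds no visits, staff or patients.

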Provide details of remuneration, when applicable. Even when subjects may derive medical benefit from participation, it is often the case that extra hospital visits, meals at the hospital, parking fees or other inconveniences will result in additional out-of-pocket expenses related to study participation. Investigators may wish to consider providing reimbursement for such expenses when funding is available

Subjects will be compensated based on the procedures undertaken. The amount of compensation will be as follows:

- Assessment/evaluation sessions: \$50 each (up to 2)
- Training sessions with the BURT: \$5 each (up to 18)

Each subject will receive up to \$190 in for completing the whole study. Additionally, we will cover the cost of parking at SRH for all the visits.

For guidance, refer to the following Partners policies:

Recruitment of Research Subjects

https://partnershealthcare-

public.sharepoint.com/ClinicalResearch/Recruitment Of Research Subjects.pdf

Guidelines for Advertisements for Recruiting Subjects

https://partnershealthcare-

public.sharepoint.com/ClinicalResearch/Guidelines For Advertisements.1.11.pdf

Remuneration for Research Subjects

https://partnershealthcare-

public.sharepoint.com/ClinicalResearch/Remuneration for Research Subjects.pdf

CONSENT PROCEDURES

Explain in detail how, when, where, and by whom consent is obtained, and the timing of consent (i.e., how long subjects will be given to consider participation). For most studies involving more than minimal risk and all studies involving investigational drugs/devices, a licensed physician investigator must obtain informed consent. When subjects are to be enrolled from among the investigators' own patients, describe how the potential for coercion will be avoided.

At the first point of contact (usually a phone call), study staff will administer a phone screening questionnaire. Phone screening questionnaires will not contain identifiable information unless the subject is eligible and agrees to attend the first visit to give informed consent. Subjects will be given the option to attend the screening in person. The procedure will start with the Mini-Mental State Examination (MMSE) for the assessment of an individual's ability to follow instructions sufficiently for the successful completion of study protocol. If the MMSE score is less than 23, the subject will be excluded from the study and the procedure will stop.

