Since it is relatively common for people to have impaired decision-making capability after a stroke, prospective study volunteers' decision-making capacity and ability to give consent will be assessed using the University of California at San Diego Brief Assessment of Consent Capacity (UBACC) Questionnaire. If the subject demonstrates that he/she is able to understand the study procedures and provide consent, we will proceed to obtain informed consent. In the event that a potential subject fails the UBACC and a surrogate is not present, we will ask the subject's permission to contact a surrogate over the phone. The consenting process will be stopped until both, subject and surrogate, are present. We will contact the surrogate, ask if they would be willing to come to the laboratory with the subject and make an appointment if they agree. We will go over the consent form in detail with the surrogate and provide them sufficient time to go over the study, ask questions and make an informed decision.

Study staff members (either the PI or a non-clinician investigator not involved in the patient's care) who have completed the human subject protection educational requirements, and the CITI Program in Protection of Human Subjects, in compliance with all Federal regulations regarding such training, will obtain informed consent in the Motion Analysis Laboratory (MAL) at SRH. The test procedures will be described to the subject. Study staff will clearly explain all the procedures and risks of the testing outlined in the informed consent form (ICF). The subject will be told that the informed consent also asks for permission to view information in their medical records (for instance images) to gain a better understanding of the characteristics of their stroke (e.g. site and severity of their stroke). They will also be told that the investigators will limit their review to already existing head CT and MRI images and reports already contained in the Electronic Medical Record system. The subject will be given adequate time to consider their decision to participate in the study and encouraged to ask questions, both during the initial interview and throughout the study. A member of the study staff will answer any questions regarding the study

at the time consent is given. Once enrolled, the subject may pause or terminate his/her participation at any time during the study.

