The subject must demonstrate to study staff obtaining the consent, an understanding of the study, that it is research and not treatment, and the risks and benefits involved in the procedures.

NOTE: When subjects are unable to give consent due to age (minors) or impaired decisionmaking capacity, complete the forms for Research Involving Children as Subjects of Research and/or Research Involving Individuals with Impaired Decision-making Capacity, available on the New Submissions page on the PHRC website:

https://partnershealthcare.sharepoint.com/sites/phrmApply/aieipa/irb

For guidance, refer to the following Partners policy:

Informed Consent of Research Subjects:

https://partnershealthcare-

public.sharepoint.com/ClinicalResearch/Informed Consent of Research Subjects.pdf

DATA AND SAFETY MONITORING

Describe the plan for monitoring the data to ensure the safety of subjects. The plan should include a brief description of (1) the safety and/or efficacy data that will be reviewed; (2) the planned frequency of review; and (3) who will be responsible for this review and for determining whether the research should be altered or stopped. Include a brief description of any stopping rules for the study, when appropriate. Depending upon the risk, size and complexity of the study, the investigator, an expert group, an independent Data and Safety Monitoring Board (DSMB) or others might be assigned primary responsibility for this monitoring activity.

NOTE: Regardless of data and safety monitoring plans by the sponsor or others, the principal investigator is ultimately responsible for protecting the rights, safety, and welfare of subjects under his/her care.

Approval of protocol, informed consent procedures, and recruitment will be obtained from the IRB during annual reviews. Because this study's procedures pose relatively low risk to subjects, monthly data and procedural reviews by the PI ([name]) in consultation with study staff will be sufficient to identify and ameliorate any potential safety issues. However, any safety concerns about the equipment or clinical protocol will be brought to the attention of the PI, [name] at the time they occur, and immediate action will be taken. [name] will be responsible for determining whether the research should be altered or stopped in the event that participant safety is at risk.

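### The protocol gives two incompatible rules for a person who fails the UBACC consent-capacity test: exclusion, or a pause until a surrogate attends and decides

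*Protocol*

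**What the plan says.** The protocol sets out screening and consent in two places.

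- **Research Design and Methods, Visit number 1.** The MMSE comes first, and a score below 23 ends the procedure. The UBACC follows. A person who shows understanding goes on to informed consent. For a person who does not: "In the event that a potential subject fails the UBACC, they will be excluded from the study".
- **Consent Procedures.** The MMSE rule is repeated: "If the MMSE score is less than 23, the subject will be excluded from the study and the procedure will stop". The UBACC is introduced as before, and the outcome for a person who passes is the same. The text for failure begins "In the event that a potential subject fails the UBACC and a surrogate is not present" and goes on to say that staff will ask permission to phone a surrogate. It continues: "The consenting process will be stopped until both, subject and surrogate, are present". An appointment is made if the surrogate agrees to come. Staff then take the surrogate through the consent form and "provide them sufficient time to go over the study, ask questions and make an informed decision".

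Consent Procedures ends with a requirement on the subject: "The subject must demonstrate to study staff obtaining the consent, an understanding of the study, that it is research and not treatment". It names no exception for a surrogate. A note from the application form follows: "When subjects are unable to give consent due to age (minors) or impaired decisionmaking capacity, complete the forms for Research Involving Children". That note goes on to name a separate form for research in people with impaired decision-making capacity.

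**The concern.** The same event, a failed UBACC, ends participation in one section and only suspends the consent process in the other. Two staff members could each follow the protocol faithfully and treat the same person differently. Whichever they did would depart from one of the two sections, so the quarterly audit of adherence described under Monitoring and Quality Assurance would have no single standard to apply.

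Whether someone who fails a capacity test may enter research is a participant-protection question. It remains one even though the device has 510(k) clearance and the protocol calls its risks minimal when it is used as instructed. The protocol itself says that impaired decision-making is fairly common after stroke, so the case is foreseeable. The answer also determines whether the form's note on impaired decision-making capacity applies to this study.

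**Working it through.** The question is one of text, so the check is a side-by-side reading.

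| Step | Visit number 1 | Consent Procedures |
|---|---|---|
| MMSE below 23 | Excluded, procedure stops | The same |
| UBACC passed | Proceed to informed consent | The same |
| UBACC failed | Excluded, no qualification | With no surrogate present, one is contacted with permission and consent is paused |
| Surrogate | Not mentioned | Attends with the subject, reviews the consent form, makes a decision |
| Exclusion for UBACC failure | Stated | Not mentioned |

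The first two rows match almost word for word, so both sections describe the same sequence. They part only at UBACC failure.

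**Could other text settle it?**

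1. *Inclusion and exclusion criteria.* Neither list mentions the UBACC or capacity to consent. Exclusion 2 concerns following instructions and sustaining attention. Exclusion 4 concerns aphasia that limits comprehension and completion of the treatment protocol. Neither decides what happens after a failed UBACC.
2. *Closing requirement of Consent Procedures.* The subject must demonstrate understanding. This fits exclusion better than the surrogate route, but it stands in the same section as that route and does not mention it.
3. *Precedence.* Neither section refers to the other or is said to govern. Both are current text.
4. *Visit schedule.* Visit 1, Visit 2, Visits 3–20 and Visit 21 give 1 + 1 + 18 + 1 = 21, the stated maximum. The return appointment with a surrogate has no place of its own in that count. It could be treated as a continuation of Visit 1, so this is weak supporting evidence only.

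**Who is affected.** Anyone below 23 on the MMSE is excluded under both sections. The conflict therefore applies only to people who score 23 or more and then fail the UBACC.

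**Size.** The protocol gives no UBACC failure rate, so no expected number can be computed. With recruitment capped at 10, each affected person would be 1/10 = 10% of a full cohort, and a larger share if fewer are recruited.

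**The case against.** The best counter-argument is that Consent Procedures never says that the surrogate signs or that a person who fails the UBACC is enrolled. It says only that consent is paused, that both people must attend, and that the surrogate decides after reviewing the form. Enrolment through a surrogate is therefore an inference. The closing requirement might also bind everyone, in which case a person who could not show understanding would not enter by either route, and the practical harm would be smaller.

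Both points have some force. They limit what can be said about the surrogate's role and about how many people would be admitted wrongly. They do not remove the conflict. Even if the surrogate only supports a second attempt at consent, Visit number 1 rules that attempt out by excluding on failure. Nor is Visit number 1 merely a shorter summary: a summary might leave out the surrogate route, but this one states a different outcome.

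The 10% figure is only the reciprocal of the recruitment cap. An excluded person can be replaced, and the number affected could be zero. It shows how much one person weighs in a cohort this small, and it implies no effect on the Fugl-Meyer or any other outcome.

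**Conclusion.** The contradiction is real and must be fixed. As written, the protocol both excludes a person who fails the UBACC and provides a way for that person's consent process to continue. The conclusion rests on the wording of the two sections and needs no assumption about failure rates. That the surrogate route is meant to lead to enrolment is the natural reading, but it is not stated. The document does not show which rule was intended. No bias in the results is claimed, nor that any required form is missing. The importance lies in participant protection and in having one rule that staff can follow and auditors can check.

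**What to change.** Adopt one rule for a failed UBACC and state it identically under Visit number 1 and Consent Procedures.

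- **If failure means exclusion:** delete the surrogate text from Consent Procedures. Visit number 1 and the requirement that the subject show understanding can then stand unchanged. The cost is possibly a few eligible people.
- **If a surrogate route is intended:** amend Visit number 1 and the closing requirement to provide for it. State who gives consent, what the subject must still demonstrate, and what happens when a surrogate is already present. Then apply the note on impaired decision-making capacity. The cost is the additional form that the note names.

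Either way this is a wording amendment with no change to design or analysis.

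A separate, minor point can be tidied in the same amendment. The consent paragraph says "Informed consent will be obtained and subjects will be enrolled in the study prior to any clinical or laboratory testing", while both descriptions of screening place the MMSE and UBACC before consent. The phrase may refer only to the later assessment battery, in which case a short clarification is enough. The main finding does not depend on it.
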